Official Title: Intense Pulsed Light Study for Dry Eye Disease

NCT03089580

Version Date: July 12th, 2019

A. Study Hypothesis and Objectives

Dry eye disease (DED) is defined as a “multifactorial disease of the tears and ocular surface that results in symptoms of discomfort, visual disturbance, and tear film instability with potential damage to the ocular surface. It is accompanied by increased osmolarity of the tear film and inflammation of the ocular surface[1].” This condition may also compromise surgical outcomes and patient satisfaction following cataract, refractive surgery[2], and corneal transplants[3]. DED can also impact everyday tasks such as reading, using a computer, driving, and watching television which can be up to three times more difficult[4]. Worker productivity is potentially adversely affected by DED and scales with disease severity[5]. In addition, depression is more prevalent in DED patients[6], further evidence of the disease’s debilitating effects. Current treatments options are limited and a recent study found 75% of DED patients report inadequate relief despite treatment. There is a critical barrier to provide efficacious treatment modalities to improve quality of life and to improve ocular surface health affected by DED.

A new treatment called Intense Pulsed Light (IPL) shows promise to reduce signs and symptoms in preliminary studies. IPL is a broad spectrum, non-coherent light treatment applied to the face and lower lids followed immediately by meibomian gland expression. Unfortunately, rigorous peer-reviewed studies on IPL are largely missing. Additional controlled, clinical studies are critical to better understand the potential of IPL to minimize objective measures of DED and improve patient quality of life.

i. Study Aim

The aim of this project is to rigorously evaluate the efficacy of IPL and to determine whether quality of life improvements can result from its implementation. Our hypothesis is that IPL can provide reduction and potential elimination of symptoms for patients with the evaporative form of DED by improving the meibomian gland expression quality and quantity resulting in a more stable, intact tear layer. We believe that the IPL treatment will deliver these results above and beyond meibomian gland expression alone.

ii. Research Goals

- a.** Substantiate the efficacy of IPL treatment for DED. Our study will collect objective measures of DED disease at baseline and after each of four IPL treatments. Our study design is a prospective, randomized, single masked trial. This evidence will assist practitioners, patients, and third parties to understand the value of this procedure and who will most likely benefit.
- b.** Determine the potential improvement in quality of life measures with IPL. DED has a substantial negative impact on quality of life. We will measure patient symptoms before and after each IPL treatment to assess the change in subjective quality of life measures using two validated questionnaires.
- c.** Demonstrate that IPL treatment improves DED above and beyond meibomian gland expression alone. There is limited evidence to support if the efficacy of IPL treatment is merely from IPL or the meibomian gland expression alone. Our proposed study is intended to clarify whether adding IPL before meibomian gland expression improves the outcomes. To our knowledge, no previous studies have addressed this question.

B. Background Information

Dry eye symptoms are common complaints in an estimated 25% of all eye doctors visits[7]. In the US population over 50 years of age, there are approximately 1.68 million men and 3.23 million women with diagnosed DED[8, 9]. The U.S. healthcare cost attributed to DED is approximately \$3.84 billion[5]. The symptoms of this disease can range from a mild annoyance to extremely debilitating. Common symptoms include burning, stinging, tearing, blurred vision, foreign body sensation, contact lens intolerance, redness, chronic pain, and photophobia. Current treatments include topical tear supplements, environmental modifications to minimize tear evaporation, punctal occlusive treatments, ocular surface barriers, lid treatments, and immunomodulatory agents. Despite these various treatments, inadequate relief is common and there is a critical barrier to provide efficacious treatment modalities to improve quality of life and to improve ocular surface health affected by DED. We propose to test the hypothesis that IPL therapy will provide relief of evaporative DED symptoms by improving meibomian gland expression.

There are two classifications of DED: aqueous deficient and evaporative[1]. There is some overlap, but the vast majority of dry eye is evaporative. Meibomian gland dysfunction (MGD) is the most common cause of evaporative dry eye. Intense Pulsed Light (DermaMed Solutions, Lenni, PA; Lumenis Ltd., Yokneam, Israel) will be applied to the lower eyelids and face with the intent to improve MGD. We will test our hypothesis and complete our goals by conducting an intervention to one eye and the fellow eye will serve as a control to compare the effects of IPL in patients who have evaporative DED due to MGD.

The study is a prospective, randomized, controlled, single masked trial. The randomization is based on IPL treatment to one eye and sham treatment to the fellow eye. The randomization will occur via a random number generator. The masking is based upon the cornea specialist's examination. The primary outcome measures include tear break up time (TBUT) and the Ocular Surface Disease Index (OSDI) symptom survey. Exploratory outcome measures will include the National Eye Institute Visual Function Questionnaire (NEI-VFQ), changes in MGD quantitated by lid margin photography and meibography before and after IPL, and other standard dry eye clinical evaluation tools.

All enrolled participants will be assigned a number, and the link between the number and participant will be secured. All data collection will comply with HIPPA guidelines. Data collection will include: clinical exam data, eyelid and facial photography, and meibography which will be de-identified.

i. Participant Eligibility Criteria

a. Inclusion Criteria

1. Willing and able to provide informed consent;
2. 18 years of age or older;
3. Diagnosed with evaporative dry eye disease with symptoms for 6 months or more;
4. Able and willing to comply with follow-up visits, phone calls and IPL treatments;
5. Agree to using an effective method of birth control during the course of the study;
6. Agree to continue current dry eye treatments during the course of the study;
7. Fitzpatrick skin scale[14] of 1 (very fair) to 4 (olive) as determined by an investigator.

b. Exclusion Criteria

1. Darker skinned individuals defined by the Fitzpatrick scale 5 and 6 as determined by an investigator;
2. Neurotrophic keratitis;
3. Ectropion, trauma, or any other lid abnormalities;
4. Previous diagnosis of Stevens Johnson syndrome or graft versus host disease;
5. Ocular burn, active ocular infection, or active ocular inflammation;
6. Currently pregnant or trying to become pregnant in the next 5 months;
7. Systemic conditions or currently taking medications which makes light therapy contraindicated (the use of doxycycline is allowed);
8. Tattoos in the treatment area;
9. Patients who have had IPL, Lipiflow or Meibothermoflo within the past six months;
10. Contact lens wear more than one time/week or history of refractive surgery;
11. Glaucoma drop use
12. Ophthalmic steroid use within the past 30 days;
13. Punctal plugs if instilled within 30 days of the start of the study;

14. Obvious asymmetry between the two eyes deemed significant by the investigators (such as punctal plugs or cautery in only one eye, etc);
15. History of a trabeculectomy or tube surgery;
16. Uncontrolled ocular or systemic disease;
17. Ocular or eyelid surgery within the last 6 months;
18. Any condition which leads the investigator to believe that the patient cannot comply with the study requirements and/or the patient may be placed at risk with participation.

ii. Study Procedures

Potential participants will provide written informed consent prior to any baseline testing (visit 1). All participants will be asked to complete 5 in-clinic study visits and 2 telephone calls over the course of approximately 7 months. Women of child bearing potential will be asked to provide a urine sample for a pregnancy test at the baseline visit. The investigator may ask for an additional pregnancy test at subsequent visits if they deem necessary.

The patients will be evaluated at baseline (visit 1) and return once a month for a total of 5 months (visits 2, 3, 4 and 5). They will be asked to complete study testing and will be evaluated by a masked corneal specialist at each visit. The phenotypic characterization for dry eye will include the following tests for both eyes: tear break-up time (TBUT) in triplicate using a timer, lissamine green staining of conjunctiva (grading 1-4, noted temporally and nasally), corneal staining with fluorescein (grading 1-4, breaking the cornea into 4 sections), meibomian gland health with the Meibomian Gland Evaluator (TearScience, Morrisville, NC), tear osmolarity, and 5-minute Shirmers under anesthetic using a timer. All patients will also undergo standardized slit lamp eyelid margin photography that includes upper and lower lids, have facial photography and meibography of the lids. Other testing that will be completed at certain time points include pinholed ETDRS visual acuity testing and the measurement of intraocular pressure. We will also obtain information about the participant's medical history (review of systems), and current ocular and systemic medications.

All participants will take the Ocular Surface Disease Index (OSDI)[15] and 25-item National Eye Institute Visual Functioning Questionnaire (NEI-VFQ)[16]. Both questionnaires will be administered at each visit. These surveys do not allow for separating the response between each eye.

The participants will also be contacted over the phone by a member of the study team approximately 1 week and 7 months after their baseline visit.

iii. Study Design

Once the patient has signed informed consent, completed the baseline testing, and is determined to be eligible by an investigator, they will have one eye randomized to receive the IPL treatment and the fellow eye will receive a sham treatment.

a. Intervention with IPL

IPulse Quadra Q4 and Lumenis M22 devices will be provided by the cornea clinic at Kellogg Eye Center.

Prior to treatment, eye shields will be placed over both eyes of the participant. On the side that was randomly selected to receive the IPL treatment, ultrasound gel will be applied around the eye, lower eyelid, cheek, side of nose and temple. The PI will then administer approximately 15 light spots in areas where the ultrasound gel was applied.

All IPL treatments will be performed by the same investigator, the PI, who will not be masked. Each subject's eyes will be randomized with one eye/side of the face receiving IPL treatment (Figure 3), and the fellow eye serving as a control. At the first IPL treatment, the energy level (range of 8-18 joules) will be individually determined based the patient's skin Fitzpatrick scale phototype. The IPL instrument, Quadra Q4®, includes four pulse levels (1-4) each with six sublevels (A-F). The pulse intensity is inversely related to the skin phototype scale, and as noted in subject inclusion and exclusion criteria above, we will only treat patients who are phototype 1 through 4. The sublevel D is used for the initial treatment unless the patient cannot tolerate it and then a lower sublevel will be used. Future treatments sublevels will be increased gradually unless the examiner determines this is unsafe for the patient.

The Lumenis M22 IPL device requires the user to input fluence (joules/cm²) level prior to treatment. The below graph shows the fluence levels of the Dermamed Quadra Q4® that correlate to the fluence levels of the Lumenis M22.

		Fitzpatrick Skin type		
	1	2	3	4
A	10J/cm ²	9J/cm ²	8J/cm ²	8J/cm ²
B	11J/cm ²	10J/cm ²	9J/cm ²	8.5J/cm ²
C	12J/cm ²	11J/cm ²	9.5J/cm ²	9J/cm ²
D	13J/cm ²	12J/cm ²	10J/cm ²	9.5J/cm ²
E	14J/cm ²	13J/cm ²	10.5J/cm ²	10J/cm ²
F	15J/cm ²	14J/cm ²	11J/cm ²	10.5J/cm ²

Figure 3. IPL treatment. After placing eye shields, an ultrasound gel is applied. Treatment spots are done around the eye, lower eyelid, cheek, side of nose and temple.

b. Sham Treatment

With the eye shields still in place, the fellow eye will be treated with approximately 15 spots of pressure around the eye, lower eyelid, cheek, side of nose and temple with the IPL device. No light energy will be applied. The PI will only place the device on the participant and press to mimic actual IPL treatment. Ultrasound gel will be applied to these areas prior to the sham treatment to prevent unmasking of the participant.

c. Post-Treatment

After the IPL and sham treatments have been completed, the eye shields will be removed, and the face cleaned. The upper and lower lids of both eyes will be expressed with a meibomian gland expressor while being positioned at the slit lamp.

After treatment, as recommended by the manufacturer, each subject will be asked to use ketorolac twice a day for three days and to wear SPF 30 sunscreen for one week. During the course of the treatment period, any adverse events will be noted per the adverse reporting guidelines outlined in section D.

d. 1 Week Safety Follow Up Phone Call (+/- 2 days)

Approximately one week after the participants have completed the baseline visit and received the IPL and sham treatments, a member of the study team will contact the participants to answer any questions and to document any adverse events.

e. Follow Up Visits (+/- 10 days)

Participants will return to the clinic for 4 additional visits after the baseline visit (visit 1).

At visits 2, 3, and 4, participants will be evaluated by a corneal specialist who is masked to the IPL treatment randomization, complete the testing outlined in the schedule of events (appendix A), and receive IPL and sham treatments accordingly. Participants will receive a total of 4 IPL and sham treatments throughout the duration of the study.

Participants will be asked to return to the clinic approximately 16.5 weeks after their baseline visit to complete visit 5. They will complete the testing outlined in the schedule of events but will not receive IPL or sham treatments.

f. 7 Month Follow Up Phone Call (+/- 5 days)

After the participant's final visit (visit 5) a member of the study team will contact the participant approximately 7 months after their baseline visit. Participants will be asked to complete the OSDI and NEI-VFQ questionnaires over the phone. After completion of the questionnaires, the study team member will inform the participant of which eye received the IPL treatment and which eye received the sham treatment. Also during this call, the participants will be offered to complete an optional visit. At this optional visit they will be asked to complete the testing outlined in the schedule of events and will be offered IPL treatment on both eyes free of charge. Patient's that do not wish to come in for the optional visit and IPL treatments, end their participation after completing the questionnaires, if they did not choose to end it sooner.

D. Reporting Procedures

i. Adverse Events

- a.** Adverse events (AEs) and complications determined by the investigator to be "possibly", "probably" or "definitely" related to the IPL treatment or study procedures will be recorded and reported to the IRB according to their reporting guidelines.
- b.** Any AE that is determined by the investigator to meet the definition of an unanticipated problem involving risks to subjects or others will be reported within 7 days to the IRB if is determined to be a serious problem. If the unanticipated problem is determined to be non-serious, it will be reported to the IRB within 14 days.

ii. Serious Adverse Events

- a.** Any AE which meets the FDA definition of serious and determined by the investigator to be "possibly", "probably" or "definitely" related to the IPL treatment or study procedures will be recorded and reported to the IRB within 7 days.

iii. Other Reportable Occurrences

- a.** All protocol deviations will be reported to the IRB at the continuing renewal.
- b.** Any privacy violation or breach of confidentiality will be reported to the IRB within 7 days and within 24 hours to the UMHS Privacy Office.

iv. Unmasking

- a.** Unmasking of the participant will occur after completion of the ODSDI and NEI-VFQ questionnaires during the 7 month follow up call.
- b.** Unmasking may occur at any time point throughout the trial if it is determined by an investigator to be in the best interest of the participant.

E. Statistical Methods

i. Sample Size and Power

The primary study outcome (pre to post change in TBUT within the treated eye and also the untreated, control eye) dictated the use of a paired statistical approach to sample size estimation. Based on our preliminary data, other published dry eye studies[17], and recent meeting abstract (ASCRS 2014; Gupta PK et al.) the expected, clinically relevant pre to post TBUT increase of 3 seconds with a standard deviation of 4.5 seconds was used. Type I and II error estimates used were standard for a non-pivotal study, 0.05 & 0.20. The estimated the sample size needed detect this difference in TBUT is 27 subjects. We will recruit 30 subjects allowing for an anticipated 10% drop-out rate.

All three study goals have a paired design wherein the first two goals contrast pre- to post-treatment measures in the treated eye, and the 3rd compares the treated eye to the control eye. The primary analysis for each objective will apply the paired, Student's t-test to contrast the continuous outcome variables for efficacy assessment (TBUT, Shirmer's test, corneal staining) in the treated eye (Goal 1) and the patient's quality of life (Goal 2), and the treated vs. control eye measures (Goal 3) from pre-treatment to post-4th treatment times. If the parametric assumptions of this test are not met, the non-parametric equivalent test, the Wilcoxon signed rank test, will be applied. In all cases, the null hypothesis to be tested is one of no change from pre- to post treatment, with a Type I error probability of 0.05 for the primary outcome assessment. The pattern of change over the 4 treatment visits in these continuous variables will be assessed using mixed, linear regression. SAS version 9.4 statistical software (SAS Institute, Cary, NC) will be used.

F. Summary and Long-Term Plan

Dry eye disease is a prevalent ocular condition with inadequate treatments available for proper relief. IPL has the potential to help those with evaporative dry eye due to meibomian gland dysfunction. This is a new treatment that needs to be studied with more rigor to understand the magnitude of the benefit for the relief of symptoms and reduced clinical signs. This study will provide answers to these questions in a prospective, masked design with the hope of providing an improved quality of life to those with DED.

We plan to use the anticipated results from this pilot study to apply for funding for a larger, prospective study on a specific population at high risk for severe DED, those with graft versus host disease. These patients often have extreme dry eye due to damage to the lacrimal and meibomian glands. Kellogg Eye Center has a large volume of these patients from the University of Michigan Cancer Center. Often the current dry eye treatments are not sufficient to effectively treat their DED. There are currently no studies on the efficacy of IPL on this population. This project would require additional funding through another grant. With addition funding, we also

hope to purchase a meibographer to image the entire meibomian glands in the tarsal plate to detect atrophic glands which are unlikely to respond to treatment.

G. References:

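### The plan names two different primary outcomes and does not make the between-eye contrast primary; OSDI, one score per patient, has no concurrent control and cannot show an IPL symptom gain beyond expression

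*Combined protocol and SAP*

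**What the plan says.** Section C, Study Design, gives two primary outcomes: "The primary outcome measures include tear break up time (TBUT) and the Ocular Surface Disease Index (OSDI) symptom survey". It lists NEI-VFQ as exploratory.

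Section E.i describes one primary outcome, TBUT, in within-eye terms: "The primary study outcome (pre to post change in TBUT within the treated eye and also the untreated, control eye" (the plan's parenthesis closes there). The sizing rests on TBUT alone: "clinically relevant pre to post TBUT increase of 3 seconds with a standard deviation of 4.5 seconds was used". Error rates are 0.05 and 0.20, the result is 27 subjects, and 30 are recruited to allow for 10% drop-out. Section E never names OSDI.

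The second paragraph of Section E assigns paired t-tests to three goals. Goals 1 and 2 are pre-to-post contrasts; Goal 3 compares the treated with the control eye. One Type I error of 0.05 is given for the primary outcome, and the null for every test is no change from before to after treatment.

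On the questionnaires, Section C.ii says: "These surveys do not allow for separating the response between each eye". Under Section C.iii, one eye of each patient is randomised to IPL and the fellow eye to sham, the lids of both eyes are then expressed, and each patient is asked to use ketorolac.

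On purpose, Section A.i wants "to determine whether quality of life improvements can result from its implementation". It hypothesises fewer symptoms through better gland expression and a more stable tear layer, then adds: "We believe that the IPL treatment will deliver these results above and beyond meibomian gland expression alone".

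**The concern.** Two things are unsettled. First, a reader cannot tell whether the trial succeeds on TBUT, on OSDI or on both, or whether the deciding test is within or between eyes. Followed literally, the plan could declare success on a pre-to-post change that makes no use of the randomisation.

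Second, one of the two named primary outcomes has no control in this design. The randomised unit is the eye and OSDI is scored per patient. Since every patient receives IPL on one side, nobody has an OSDI score under expression alone. A fall in OSDI mixes IPL with expression, ketorolac, expectation, regression to the mean and time. Gel is applied "prior to the sham treatment to prevent unmasking of the participant", but this hides only which side was treated. Every patient is treated, so expectation stays in a whole-patient score.

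At stake is the question the trial exists to answer: whether IPL adds anything to expression.

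**Working it through.** **1. The passages side by side.**

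| Place | Primary outcome | Contrast |
|---|---|---|
| Section C | TBUT and OSDI | not stated |
| Section E.i, first paragraph | TBUT only | pre to post, within each eye |
| Section E, second paragraph | a single primary outcome at 0.05, not named | null of no pre-to-post change for all goals, although Goal 3 compares eyes |

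These cannot all hold. Both eyes could improve equally: the stated null would then be false in each eye while IPL added nothing. The null that fits Goal 3 is no difference between eyes in change.

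**2. Which measures have a control.** TBUT is measured in both eyes by a masked corneal specialist (Appendix A, footnote b), so the fellow eye is a randomised, sham-treated comparator. OSDI and NEI-VFQ have none. No sample size alters that.

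**3. Two primaries at 0.05.** If success on either counted, the error is at most 0.05 + 0.05 = 0.10, and 1 − 0.95² = 0.0975 if the tests were independent. The plan states no rule.

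**4. The plan's own figure.** Inputs from Section E.i: difference 3 s, SD 4.5 s, alpha 0.05 (two-sided assumed, since sidedness is not stated), power 80%.
- Normal approximation: n = ((1.960 + 0.842) × 4.5 / 3)² = 17.7, so 18. The exact paired t-test needs 20.
- The stated 27 is not reproduced. With these inputs, 27 pairs give 91.5% power.
- The drop-out step reproduces: 27 / 0.9 = 30.
- With 27 pairs, 80% power corresponds to 0.560 SD of the paired difference. For 3 s, that implies an SD of 3 / 0.5601 = 5.36 s.

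The plan does not say which SD 4.5 s is, so both readings are carried forward.

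**5. What the between-eye test can detect.** SD of the between-eye difference in change = SD of each eye's change × √(2(1 − r)), where r is the between-eye correlation of change. The detectable difference at 80% power is 0.560 times that. The plan gives no r, so the values below are assumed.

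| r | SD of difference if each eye's SD is 4.5 s | Detectable | SD of difference if each eye's SD is 5.36 s | Detectable |
|---|---|---|---|---|
| 0.3 | 5.32 s | 2.98 s | 6.34 s | 3.55 s |
| 0.5 | 4.50 s | 2.52 s | 5.36 s | 3.00 s |
| 0.7 | 3.49 s | 1.95 s | 4.15 s | 2.32 s |

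Power for a full 3 s between-eye difference is 80%, 92% and 99% on the first reading, and 66%, 80% and 95% on the second.

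**6. What an uncontrolled test would do.** The plan gives no SD of OSDI change, so this is hypothetical. With no IPL effect and n = 27, a shift from other causes of 0.1, 0.2, 0.3 or 0.5 SD would be significant in 8%, 17%, 32% or 71% of trials.

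**The case against.** The plan is open about the questionnaires. It says that they are not eye-specific, tests quality of life only pre to post, and reserves the control comparison for eye measures. A reader might infer that a between-eye OSDI test is planned; none is. What remains is OSDI's primary status and the conclusion that might be drawn from it.

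A reader might also infer that the protocol plainly promises a symptom gain beyond expression. In Section A.i, the results referred to include gland expression and tear-film stability as well as symptoms, and goal c, which takes up the comparison with expression, speaks of improving DED without naming symptoms. Goal b, "Determine the potential improvement in quality of life measures with IPL", goes on to describe its aim as assessing change. Rewording these would add little.

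A third tempting inference is that TBUT is as uncontrolled as OSDI. It is not: Section E.i names change in both eyes, and Goal 3 compares them.

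It is also fair that the illustrations rest on assumed shifts and correlations, and that moving the primary test changes what 27 pairs can show. If the control eye gained 1 s (assumed), the remaining 2 s would have 47%, 60% or 82% power with SD 4.5 s; 80% power would need 58, 42 or 26 pairs. That stands as a cost. The pilot, non-pivotal setting lowers the stakes, but the plan should still say which result decides success.

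**Conclusion.** The point holds on the text, without the power figures. The primary outcome is inconsistent between Sections C and E.i; the blanket pre-to-post null does not fit Goal 3; and OSDI has no concurrent control, so it cannot show a symptom gain from IPL beyond expression.

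The documents do not support reading this as an invalid trial. The randomised TBUT comparison is already planned, and the right data are collected for it. Nor do they show that 27 is too few: that depends on which SD 4.5 s is and on a correlation the plan does not give. Across the assumed range, the detectable between-eye difference runs from 1.95 to 3.55 s. This should be fixed before results are interpreted.

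**What to change.** Reconcile Sections C and E:

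- Make the treated-minus-control-eye difference in TBUT change, from baseline to after the fourth treatment, the primary test at 0.05, with a null of no difference between eyes in change.
- List OSDI as secondary under Goal 2. Report OSDI, NEI-VFQ and the Goal 1 within-eye changes with 95% confidence intervals, labelled uncontrolled.
- If OSDI stays primary, label it uncontrolled and state how 0.05 is shared between the two outcomes.
- Restate the justification for 27 on the between-eye difference, saying which SD 4.5 s is and giving the assumed between-eye correlation.
- As an editorial tidy-up, Section E's description of Goal 2 as a treated-eye contrast should go, since the surveys are per patient.

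The cost is wording. Visits, tests and questionnaires are unchanged, and enrolment need not change. The sponsor gives up an IPL-specific symptom claim, and the between-eye test has less power than the pre-to-post test if the control eye also improves.

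### No stable-regimen period is required before visit 1, so gains from a recently started dry eye therapy could enter the before-after changes for Goals 1 and 2

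*Combined protocol and SAP*

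**What the plan says.** Section C.i.a, inclusion 6, requires participants to "Agree to continue current dry eye treatments during the course of the study". This looks forward only. Inclusion 3, "Diagnosed with evaporative dry eye disease with symptoms for 6 months or more", sets a duration for symptoms, not for treatment.

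The therapy look-back rules are all in Section C.i.b:

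- Exclusion 9: "Patients who have had IPL, Lipiflow or Meibothermoflo within the past six months".
- Exclusion 12: "Ophthalmic steroid use within the past 30 days".
- Exclusion 13: "Punctal plugs if instilled within 30 days of the start of the study".

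Exclusion 7 states that "the use of doxycycline is allowed", with no condition on how long it has been taken. Section B describes the therapies patients may be using: "Current treatments include topical tear supplements, environmental modifications to minimize tear evaporation, punctal occlusive treatments, ocular surface barriers, lid treatments, and immunomodulatory agents". Of these, only punctal plugs have a pre-baseline rule.

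Appendix A places baseline testing, randomisation and the first treatment at visit 1, with no run-in. Medications are reviewed at visits 1 to 5, but Section E.i makes no use of that record. Section E.i tests Goals 1 and 2 as change from before treatment to after the fourth treatment, against a null of no change, and compares treated with control eye for Goal 3. Section C names TBUT and OSDI as primary outcome measures, and Section C.ii notes that the questionnaires cannot be answered separately for each eye.

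**The concern.** A patient who began an immunomodulatory drop, a lid treatment or doxycycline the week before visit 1 is eligible and then agrees to stay on it. That patient's baseline is measured while another therapy may still be taking effect, and visit 5 follows at about 16.5 weeks. Any improvement from that therapy is part of the change that Goals 1 and 2 test.

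The exposure is greatest for OSDI and NEI-VFQ. Each gives one score per person, so nothing measured at the same time separates background drift from the effect of study treatment. The Goal 1 test on the treated eye also uses no control, although control-eye TBUT is measured. The protocol already applies a stability rule to one continuing therapy, punctal plugs, and gives no reason for leaving out the others.

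**Working it through.** **Does any criterion close the gap?** Inclusion 3 concerns symptoms. Exclusions 9, 12 and 13 cover only the therapies they name. Exclusion 17 (six months) concerns surgery. Exclusions 5 and 16 (active inflammation, uncontrolled disease) and 14 (obvious asymmetry between eyes) narrow the population, but none concerns time on treatment. The gap stands for tear supplements, lid treatments, immunomodulatory agents and doxycycline.

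**Inputs from Section E.i.** TBUT increase 3 s, SD 4.5 s, Type I error 0.05, Type II error 0.20, 27 subjects (30 recruited). I take 4.5 s as the SD of the before-after change and the test as two-sided; the plan does not state sidedness.

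**The plan's own figure.** n = [4.5 × (1.960 + 0.842) / 3]² = 17.7, so 18 by the normal formula and 20 by the exact t calculation, not 27. The step 27 / (1 − 0.10) = 30 does reproduce. The mismatch is a separate matter. I use 27 below only as the planned number completing.

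**Assumptions.** The documents give neither the share f of recent starters nor their gain g. I take f from 10% to 33%, g from 1 to 3 s for TBUT, and 5 to 10 points for OSDI.

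**TBUT.** Mean inflation is m = f × g. With no other source of change, the SD of the change is s = √[4.5² + f(1 − f)g²]. The rejection probability comes from the noncentral t distribution with 26 degrees of freedom and noncentrality √27 × m / s.

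Example: f = 0.33 and g = 3 give m = 0.99 s, s = √(20.25 + 1.99) = 4.72 s, noncentrality 5.196 × 0.99 / 4.72 = 1.09, and rejection probability 0.183.

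| Share f | g = 1 s | g = 2 s | g = 3 s |
|---|---|---|---|
| 10% | 0.10 s; 0.051 | 0.20 s; 0.056 | 0.30 s; 0.062 |
| 20% | 0.20 s; 0.056 | 0.40 s; 0.072 | 0.60 s; 0.099 |
| 33% | 0.33 s; 0.065 | 0.66 s; 0.111 | 0.99 s; 0.183 |

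Each cell gives the mean inflation, then the probability of rejecting the before-after null when nothing but the background therapy moves TBUT. Against the planned 3 s, the inflation runs from 0.10 / 3 = 3% to 0.99 / 3 = 33%.

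**OSDI.** Inflation runs from 0.10 × 5 = 0.5 to 0.33 × 10 = 3.3 points. The preliminary fall in Section B.i was 23.79 − 12.4 = 11.39 points, so this is 0.5 / 11.39 = 4% to 3.3 / 11.39 = 29% of it. No SD for OSDI change is given, so no error rate can be computed.

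**Between-eye contrast (Goal 3).** In 20,000 simulated trials per setting (27 subjects, SD 4.5 s, assumed between-eye correlation 0.5, no IPL effect), both eyes received the same shift of 0, 1.5 or 3 s. The before-after test rejected with probability 0.05, 0.39 and 0.92. The treated-minus-control test stayed at about 0.05 throughout.

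**The case against.** The strongest reply is that the causal question, whether IPL adds to gland expression, rests on the randomised between-eye comparison, and that comparison is largely unaffected. This stands. A reader might infer that the missing rule biases IPL against sham on TBUT, or uses up room to improve in both eyes. The documents support neither: a shared shift cancels within the person, and no TBUT ceiling is documented (the preliminary mean rose from 1.05 to 5 s).

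Second, a stable regimen would not turn the Goal 1 and 2 changes into an IPL effect. They also contain expression of both eyes' lids, expectation and regression to the mean, and ketorolac is used after each treatment. This also stands: unstable therapy is one component among several. It is, however, one that an eligibility line can remove. For TBUT, the control eye would show such drift if it were examined. OSDI and NEI-VFQ offer no such check.

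Third, the plan only permits recent starters. A reader might infer that they will be common because IPL candidates have usually just changed treatment. No rate is documented. Section A's statement that 75% of patients report inadequate relief despite treatment makes recent changes plausible but does not measure them.

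Finally, this is a 30-subject study that describes itself as non-pivotal and a pilot. That limits how much weight the point deserves; it does not close the gap.

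**Conclusion.** The concern holds in a limited form. The criteria admit patients who have just started most background dry eye therapies, and any resulting gain would enter the before-after changes for Goals 1 and 2, including OSDI, a named primary outcome measure without a fellow-eye control. Under the assumed ranges the inflation is small to moderate for TBUT (about 0.1–1.0 s) and for OSDI (about 0.5–3.3 points). These figures depend on the assumed share and gain, and the TBUT error rates also assume an otherwise null change. The cancellation in Goal 3 assumes that the background therapy acts equally on both eyes. The amendment is worth making because it is cheap. The point does not undermine the randomised TBUT comparison.

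**What to change.** Reword inclusion 6 to require an unchanged ocular and systemic dry eye regimen for a sponsor-set period before visit 1, with no new dry eye therapy planned before visit 5. The documents do not derive a particular length; the 30 days used for steroids and plugs is a precedent, not a calculation.

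Record therapy start dates in the medication review already scheduled at visit 1. In Section E.i, add a report of the Goal 1 and Goal 2 changes with and without participants who started or changed a dry eye therapy within the set period before visit 1 or between visits 1 and 5. The pre-visit-1 part is needed: someone who started the week before baseline and then continued shows no change between visits 1 and 5.

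The cost is an eligibility amendment, one more question at visit 1, and a wait for patients not yet on a settled regimen. If enrolment is already advanced, start dates and the sensitivity analysis can still be added.
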